##### **5.1.2.Exclusion criteria**

The following exclusion criteria will apply in the observational study:

- Ultrasound examination not feasible, e.g., due to electricity breakdown, or physical absence or unavailability of the trained sonographers.

**Table 1.** Inclusion categories as defined by National Protocols and Guidelines for Emergency Obstetric and Newborn care (14) or hospital protocol.

Inclusion criteria	Case Definition
Vaginal bleeding in early pregnancy	Vaginal bleeding or cramping, with amenorrhea or positive pregnancy test <22 weeks of gestation
Pre-eclampsia	Blood pressure $\geq 140/90$ (at least 2 recordings, 4 hours apart) PLUS any of: proteinuria (at least 2+ on dipstick, headache, generalized oedema, visual disturbance).
APH third trimester:	Vaginal bleeding after 22 weeks of pregnancy or in labour before giving birth. May have final diagnosis of abruptio placentae, placenta previa and ruptured uterus.
Prolonged/ Obstructed labour:	Prolonged latent or active phase, cephalopelvic disproportion, obstructed labor, inadequate uterine activity, prolonged expulsive phase.
High risk pregnancy in ANC	Fulfil any of the following criteria (as defined by hospital protocol): 
 
1. Previous Cesarean Section
 
2. Previous still birth
 
3. Age below 18 years
 
4. Short stature (height < 150cm)
 
5. Grand Multipara: Gravida more than 5.
 
6. Fundal Height >40cm
 
7. Suspected breech
 

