#### **4.1.2. Secondary Objectives**

1. To assess the reliability for each pre-defined ultrasound finding.
2. To ascertain if the reliability varies between naïve and intermediate operators.

3. To establish the feasibility of examinations and quality of images acquired with the hand held apparatus.

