#### **4.1.4.Secondary hypothesis**

1. The diagnostic accuracy will be significantly higher for specific 'easier to detect' *individual ultrasound findings* such as intrauterine pregnancy, amniotic fluid estimation, cephalic presentation, and presence of abdominal fluid.
2. The diagnostic performance of the ultrasound *naïve operator* is significantly different from the intermediate operator only for more complex ultrasound findings such as fetal heart, presence of retroplacental hematoma, placenta location, estimation of gestational age and detection of multiple pregnancy.
3. The proportion of complete examinations is >90% and quality of images as estimated by a simple visual scoring system is high (more or equal to 3).

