## **5.2. Sample size calculation**

Sufficient information to perform a formal sample size calculation is lacking. During a 2-month period all patients meeting the inclusion and exclusion criteria will be recruited. Based on current rates of admissions in the mentioned services, we expect to recruit at least 300 patients (75 patients per operator, 15 for each of the 5 inclusion categories) during a 2 months data collection period.

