#### **6.1.2. Secondary study parameters/endpoints**

1. Detailed diagnostic accuracy for each of the nine ultrasound findings.
2. Inter-observer agreement on ultrasound findings between naïve and intermediate operators.
3. Mean 'quality of image score' (0-4) for each of the nine ultrasound findings.
4. Proportion of complete ultrasound examinations i.e. with all pre specified findings allocated for the category being completed.

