## 6.4. Safety consideration and follow up

### 6.4.1. Withdrawal of individual subjects

Patients can leave the study at any time for any reason if they wish to do so without any consequences. The investigator can decide to withdraw a subject from the study

for urgent medical reasons, e.g. when it becomes impossible to perform the ultrasound examination or this is deemed to interfere with patient care.

The study participants have the right to contact the ethics and review committee if they raise any issue or concern with the study (Office of the Sierra Leone Ethics and Scientific Review Committee, Ministry of Health and Sanitation, Directorate of Policy, Planning & Information (DPPI) [name]).

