## **7.2. Statistical analysis**

Data will be reported as mean and standard deviation or median with interquartile range (continuous data), and as frequency and percentage (categorical data). The agreement between the hand-held device and the conventional apparatus on categorical findings scoring will be assessed using diagnostic accuracy and Cohen's K statistics. When appropriate, comparison between subgroups will be performed using Student's t test, ANOVA, Mann-Whitney test or Kruskal-Wallis test for continuous data, and with Chi-square test or Fisher's test for categorical data. A p-value less than 0.05 will be considered statistically significant. Statistical analyses will be performed using R (R Foundation for Statistical Computing, Vienna, Austria). The sensitivity, specificity, positive predictive value, and negative predictive value for each dichotomous ultrasound finding acquired with hand held devices against the reference diagnoses with conventional apparatus will be assessed when appropriate. Quality of images will be assessed by standardized scoring system from 0 to 4 (0= no meaningful images; 1 = poor, not sufficient for interpretation; 2 = good, acceptable for interpretation; 3= excellent, minor suggestions for interpretations; 4 = outstanding, no suggestions for interpretations). All analyses will be conducted after the end of patient recruitment and no interim analyses are planned.

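### Total failures of the hand-held scan can leave the feasibility endpoint unrecorded, because infeasible examinations are excluded (5.1.2) and may be withdrawn (6.4.1)

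*Protocol*

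**What the plan says.** Five places in the protocol bear on this point.

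- **Objective.** Section 4.1.2, third secondary objective: "To establish the feasibility of examinations and quality of images acquired with the hand held apparatus".
- **Hypothesis.** Section 4.1.4, third item: "The proportion of complete examinations is >90" per cent.
- **Endpoint.** Section 6.1.2, fourth item: "Proportion of complete ultrasound examinations i.e. with all pre specified findings allocated for the category being completed". No denominator of eligible women is given.
- **Eligibility.** Section 5.1.2 has one exclusion criterion: "Ultrasound examination not feasible, e.g., due to electricity breakdown, or physical absence or unavailability of the trained sonographers". Section 5.2 then says "During a 2-month period all patients meeting the inclusion and exclusion criteria will be recruited", so a woman caught by this criterion is not in the study.
- **Withdrawal.** Section 6.4.1 allows the investigator to withdraw a subject "when it becomes impossible to perform the ultrasound examination or this is deemed to interfere with patient care".

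The only log described (section 7.1) links study codes to names. The protocol does not provide for recording women who were excluded because scanning was not feasible.

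**The concern.** A study that sets out to measure feasibility should not select its patients on feasibility. When the hand-held examination cannot be done at all, that is a failure the third objective ought to see. Under 5.1.2 such a woman may never enter the study, and under 6.4.1 she may leave it. The completeness proportion is then taken among women in whom scanning was at least possible, and is compared with a fixed bar of 90%.

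Such cases are foreseeable. Section 3.4 describes an unstable power supply that affects ultrasound at this hospital, and 5.1.2 itself names power failure and missing operators. At stake is what a result above 90% would mean: that the device can be used in the women for whom it is intended, or only that scans which could be started were usually finished. A later analysis plan cannot repair this if the excluded women were never recorded.

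**Working it through.** **The plan's own figure.** Section 5.2 expects at least 300 patients: 15 per category × 5 categories = 75 per operator, and 75 × 4 operators = 300. This reproduces. It is a recruitment forecast and not a power calculation.

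**Inputs.** The bar of 90% comes from 4.1.4 and n = 300 from 5.2. Two quantities are not in the protocol and are assumed: *c*, completeness among women kept, and *f*, the share of eligible women excluded or withdrawn as infeasible. For this illustration every such woman is taken to be a hand-held failure.

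**Formula.** Completeness over all eligible women = *c* × (1 − *f*). For any *f* above 0 this is lower than *c*, so under the assumption the reported figure errs only upwards. It falls to 90% at *f* = 1 − 0.90/*c*.

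| Reported *c* | *f* = 2% | *f* = 5% | *f* = 10% | *f* at which the true figure is 90% |
|---|---|---|---|---|
| 92% | 90.2% | 87.4% | 82.8% | 1 − 0.90/0.92 = 2.2% |
| 95% | 93.1% | 90.25% | 85.5% | 1 − 0.90/0.95 = 5.3% |
| 98% | 96.0% | 93.1% | 88.2% | 1 − 0.90/0.98 = 8.2% |
| 100% | 98.0% | 95.0% | 90.0% | 10.0% |

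**In counts.** 285/300 = 95.0% becomes 285/317 = 89.9% once 17 unrecorded hand-held failures are added. 300/300 becomes 300/334 = 89.8% with 34.

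**Chance of a misleading pass.** Suppose completeness over all eligible women is exactly 90%, so that the hypothesis of more than 90% is false. Among the women kept it is then 0.90/(1 − *f*). The exact binomial probability that 300 kept women show more than 90% (at least 271 complete) is:

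- *f* = 0: 47%
- *f* = 2% (0.90/0.98 = 91.8%): 85%
- *f* = 5% (0.90/0.95 = 94.7%): 99.9%

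Section 7.2 says only "A p-value less than 0.05 will be considered statistically significant" and names no test against 90%. If an exact one-sided 2.5% test were used (an assumption; success needs at least 281 of 300), the false-pass rates would be 1.7%, 14.5% and 83%.

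**If not all exclusions are hand-held failures.** Suppose only 10 of the 17 women in the first count were hand-held failures, and the other 7 lost only the reference scan and are left out of the sum. The figure is then 285/310 = 91.9%, still above 90%. The split between the two scans therefore decides the answer, and the protocol does not have it recorded.

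**The case against.** The strongest reply is that the endpoint counts examinations, not women. It asks whether an operator who scans can obtain every finding listed for the category. A scan that is started and lacks a finding still counts as incomplete, so the endpoint keeps a real class of failures. This stands. A reader might infer that the >90% result is guaranteed by construction; the definition in 6.1.2 does not support that.

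Second, many exclusions may concern the reference scan. Section 3.4 ties the unstable electricity to the existing machine, whereas the Appendix (Power Source) gives the probe a USB supply and an estimated 120 minutes on a full battery. The operators named in 5.1.2 could be the experts: 6.3.1 uses the word sonographer for the expert trainer, while sections 1 and 6.3.2 call the hand-held users physicians or medical officers. Dropping women who lost only the reference scan does not mechanically raise hand-held completeness. This also stands, and it is why the criterion must say which scan it means.

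Third, 6.4.1 is permissive and does not say that withdrawn women leave the denominator, and a statistical analysis plan that is not shown may settle that. Bias by this route is possible, not established.

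Fourth, counting every eligible woman who arrives when no operator is on duty as an incomplete scan could mainly measure study staffing. The hospital's 9,000 admissions a year (section 2.1) are about 9,000 × 2/12 = 1,500 in two months, against at least 300 expected recruits and four operators; the share meeting Table 1 is not given. This is a fair warning about the remedy, and the fix below keeps the two quantities apart.

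**Conclusion.** The point holds in a limited form. As written, hand-held examinations that fail totally can drop out of the completeness endpoint without trace, and any such loss moves the result towards the >90% hypothesis. The direction is certain only for hand-held failures. The size is unknown, because the protocol gives no infeasibility rate. If all excluded women were hand-held failures, 5.3% excluded would be enough to bring a reported 95% down to 90% of eligible women, and 2.2% would be enough for a reported 92%.

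A reader might go further and infer that the accuracy results are biased in the same way. The documents do not support that as a fault of this plan: accuracy needs both scans, so restricting it to pairs is inherent in the design. The primary endpoint is not touched by this point. The problem affects the last of four secondary endpoints, so it is a should-fix and not a must-fix. It needs doing before recruitment, since unrecorded exclusions cannot be recovered.

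**What to change.** 1. **Section 5.1.2.** State which scan the criterion refers to. Infeasibility of the hand-held scan for device, power or patient reasons should not be an exclusion.
2. **Sections 6.1.2 and 6.4.1.** For the completeness endpoint, count a hand-held scan as incomplete if it was attempted without obtaining all findings, was abandoned, could not be started for the reasons in item 1, or was withdrawn as impossible or as interfering with care. This changes only the counting; when procedures stop remains as the protocol has it.
3. **Reference scan only.** Where only the conventional scan fails, keep the hand-held scan for completeness and image quality, and omit it from accuracy alone.
4. **Log.** Keep one line for each Table 1 woman not scanned, with the reason: device, power, operator absent, or reference scan.
5. **Reporting.** Give coverage of all eligible women as a separate figure beside completeness, so that operator absence is visible but not merged with feasibility of the device.

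The cost is a short log, new wording in three sections, and possibly a lower completeness figure.

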### **6.3. Study procedures**

#### **6.3.1. Training of operators**

The ultrasound operators will receive a 2-week training course. The 1st week training consists of lectures on basic science of ultrasound and tomography, demonstrations by an expert obstetrics sonographer, and hands-on practice at the scanning room of PCMH. The second week of training will focus on how to operate the hand-held ultrasound device, training on the standard operating procedure (SOP) and case report form (CRF) completion.

**Table 2. Ultrasound findings.** Abbreviations: GA, gestational age; FH, fetal heart; MVP, maximum vertical pocket, APH, antepartum hemorrhage; ANC, antenatal clinic.

	Inclusion category	Finding 1	Finding 2	Finding 3	Finding 4
1	Vaginal bleeding in early pregnancy	Intra-uterine pregnancy: yes/no	FH: yes/no	Free fluid in abdomen: yes/no	None
2	Pre-eclampsia	FH: yes/no	Amniotic fluid MVP<2cm: yes/no	GA: ≤34 or >35 weeks	Cephalic presentation: yes/no
3	APH in third trimester	Placenta low lying: yes/no	FH: yes/no	Retroplacental hematoma: yes/no	Amniotic Fluid MVP<2cm: yes/no
4	Prolonged/ obstructed labor	FH: yes/no	Multiple pregnancy: yes/no	Cephalic presentation: yes/no	Amniotic Fluid MVP<2cm: yes/no
5	ANC High Risk Pregnancy*	Cephalic presentation: yes/no	Multiple pregnancy: yes/no	FH: yes/no	Amniotic Fluid MVP<2cm: yes/no
				Placenta low lying: yes/no	GA: ≤34 or >35 weeks

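### The high-risk ANC category has no gestational limit but is scored on a GA class cut at 34/35 weeks and on presentation, which flatters the GA result and only slightly moves the composite

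*Protocol*

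**What the plan says.** Table 1 (printed under Protocol section 5.1.2) defines the high-risk ANC category by a list: "Fulfil any of the following criteria (as defined by hospital protocol". Criteria 1 to 5 are history or maternal traits, for example "Previous Cesarean Section", and can be met at any gestation. Only fundal height above 40 cm and "Suspected breech" point to late pregnancy, and neither is required.

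The two bleeding categories in the same table do carry a limit. One reads "Vaginal bleeding or cramping, with amenorrhea or positive pregnancy test <22 weeks of gestation" and the other "Vaginal bleeding after 22 weeks of pregnancy or in labour before giving birth". Section 5.1.1 sets no gestational limit, and the only exclusion criterion is "Ultrasound examination not feasible, e.g., due to electricity breakdown, or physical absence or unavailability of the trained sonographers".

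Table 2 (under section 6.3.1) scores the row "ANC High Risk Pregnancy" on six findings: "Cephalic presentation: yes/no", multiple pregnancy, fetal heart, a fluid pocket (MVP) under 2 cm, low-lying placenta, and GA class (at most 34 or more than 35 weeks). The early-bleeding row is scored on intra-uterine pregnancy, fetal heart and free fluid only.

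Section 6.1.4 makes recruitment consecutive, and section 5.2 takes all eligible women over two months. Section 6.1.3 lists the data to be collected and has no separate gestation item.

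**The concern.** As the tables stand, a woman at 14 weeks who is bleeding gets the early checklist, while a woman at 14 weeks with a previous cesarean gets one that includes GA class and presentation.

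For GA the consequence follows from the cut itself. Someone 20 weeks below it is placed in the lower class by both machines, however poorly the hand-held measurement was made. That agreement counts as accuracy but carries no information on device or operator.

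This touches secondary endpoint 1 (accuracy per finding). It also touches secondary hypothesis 2 in section 4.1.4, which names GA estimation among the complex findings expected to separate naïve from intermediate operators. Automatic agreements shrink that contrast.

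Presentation raises a smaller issue. In very early pregnancy the fetus may change position between the two scans, and the disagreement would then be booked as operator error.

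**Working it through.** **Planned numbers (section 5.2).** 4 operators × 75 = 4 × 5 categories × 15 = 300, so the plan's figure reproduces. That gives 60 women per category.

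**ANC share of each finding (counted from Table 2 at 60 per category).**

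| Finding | All answers | From ANC | Share |
|---|---|---|---|
| GA class | 120 | 60 | 50% |
| Low-lying placenta | 120 | 60 | 50% |
| Multiple pregnancy | 120 | 60 | 50% |
| Cephalic presentation | 180 | 60 | 33% |
| MVP under 2 cm | 240 | 60 | 25% |
| Fetal heart | 300 | 60 | 20% |

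**GA accuracy with early ANC women kept.** Let a be the accuracy in women for whom the class is in real doubt, and f the share of the 60 ANC women plainly below the cut. The protocol gives neither, so both are assumptions. All 60 pre-eclampsia women are taken to have accuracy a.

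Observed accuracy = [(120 − 60f)·a + 60f] / 120 = a + 0.5·f·(1 − a).

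- Smallest case: f = 0.25, a = 0.90 gives 0.5 × 0.25 × 0.10 = 1.25 points of inflation.
- Middle case: f = 0.50, a = 0.80 gives 0.5 × 0.50 × 0.20 = 5 points (0.80 reads as 0.85).
- Largest case: f = 0.75, a = 0.70 gives 0.5 × 0.75 × 0.30 = 11.25 points.

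**Kappa, middle case.** Assume the other 90 women are split evenly at the cut with symmetric errors. The cells are 36, 9, 9 and 36 + 30 = 66. Observed agreement is 102/120 = 0.85. Chance agreement is 0.375² + 0.625² = 0.531. Kappa = (0.85 − 0.531)/(1 − 0.531) = 0.68, against 0.60 with no early women. At a = 0.80, f = 0.25 and f = 0.75 give 0.64 and 0.71. So kappa does not remove the effect.

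**Operator contrast.** Each operator expects 15 ANC women among 30 scored on GA, so the same formula applies and a true difference in a is multiplied by 1 − 0.5f. At f = 0.50, operators at 0.70 and 0.90 would show 0.775 and 0.925: a gap of 15 points instead of 20.

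**Primary endpoint.** GA is one of nine findings. In an unweighted mean the shift is 1.25/9 = 0.14 to 11.25/9 = 1.25 points. If all 1,260 answers are pooled instead, it is 1.25 × 120/1,260 = 0.12 to 11.25 × 120/1,260 = 1.07 points.

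**What a 22-week limit would change.** Assume gestation is spread evenly, the difference between the two scans is normal with SD 2 weeks, and there is one cut at 34.5. The disagreement rate is close to 0.798 × SD / (width of the range).

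- 12–40 weeks: 1.596/28 = 5.7%, so accuracy is 94.3%.
- 22–40 weeks: 1.596/18 = 8.9%, so 91.1%.
- 30–39 weeks: simulation gives 82.5% (the approximation, 1.596/9 = 17.7%, is slightly high in a narrow band).

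With the 60 pre-eclampsia women assumed at 22–40 weeks, pooled GA accuracy is (94.3 + 91.1)/2 = 92.7% as written and 91.1% with ANC limited to 22 weeks. That is 1.6 points on GA and 1.6/9, about 0.2 points, on the composite. For SD 1.5 to 2.5 weeks the simulated gap between 12–40 and 30–39 weeks is 9 to 14 points. Most of it lies between 22 and 30 weeks, which a 22-week limit leaves in.

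**The case against.** The strongest reply is that the protocol measures agreement between two machines in the women the hospital actually sees. Section 3.5 names high-risk ANC pregnancies among its scenarios, and recruitment is consecutive. The true ANC mix is then the intended population, and dropping easy cases is a choice of spectrum. This stands as a reason to keep enrolling these women. It does not make a GA figure informative when part of it cannot go wrong.

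A reader might infer that early women distort sensitivity and predictive value for fluid, because a small pocket early on is not pathological. The documents do not support that. Section 7.2 defines these measures against the conventional scan, so a pocket under 2 cm on both machines is a correct positive. Fluid and placenta answers remain valid agreement data and lose only clinical meaning.

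A reader might also infer that the composite reflects the ANC mix rather than the device. The shift computed above is too small for that.

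The early-bleeding checklist is only partial support. It is built around a bleeding complaint and also omits multiple pregnancy, so an omission there does not prove that a finding is meaningless early.

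The ANC row carries an asterisk whose note is not in the text available, and the hospital protocol behind the criteria is not shown. Either might narrow the category. The word parturients does not, because the protocol applies it to a population that includes women below 22 weeks.

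Finally, an analysis plan could stratify by gestation. But the collected-data list has no gestation item and Table 2 asks only for a two-class GA, so as listed the data may not allow it.

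**Conclusion.** The point holds in a limited form. Tables 1 and 2 do not agree on which pregnancies the late-pregnancy findings are meant for. Women far below 34/35 weeks add GA agreements that say nothing about skill.

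The direction is certain for GA; the size is not. It is about 1 to 11 points on GA accuracy for assumed early shares of 25% to 75% and true accuracies of 70% to 90%, and 0.1 to 1.3 points on the nine-finding mean. The damage is to the GA secondary endpoint and to the operator comparison on GA.

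For presentation, extra disagreement in very early pregnancy is possible, but the documents give no figure and no interval between scans, so it cannot be sized.

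The 94% versus 83% contrast should not be read as the error in the plan. It applies an ANC-type spread to every woman scored on GA and compares it with a band chosen for illustration.

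**What to change.** 1. Add one CRF field for gestation by dates or fundal height, completed before the hand-held scan.
2. Reconcile the ANC rows of Tables 1 and 2 by stating from which gestation presentation and GA class count and, if the investigators agree, MVP and placenta. The protocol's own 22-week boundary is one candidate; the choice is theirs. Fetal heart and multiple pregnancy can be scored throughout, and enrolment need not change.
3. Because women at 22 to 30 weeks are also plainly below the cut, report GA accuracy and kappa additionally in a prespecified band around 34/35 weeks, for example 30 to 39 weeks, and show the naïve-versus-intermediate comparison on GA there too.

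The cost is one form field and one line in each table. Fewer ANC answers will count for the restricted findings, estimates in the band will be less precise, and the GA figure will look less favourable.
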